6.3 Dose Reductions

Dose reductions with regards to changes in the concentrations of talimogene laherparepvec are not permitted.

- Patients may require a reduction in the volume injected due to a disease response as outlined in Section 5.1.
- Additionally, subjects who miss two consecutive doses of talimogene laherparepvec due to a DLT should be reduced to a biweekly dosing (dose -1 as in section 5.1).

7. ADVERSE EVENTS: LIST AND REPORTING REQUIREMENTS

Adverse event (AE) monitoring and reporting is a routine part of every clinical trial. The following list of AEs (Section 7.1) and the characteristics of an observed AE (Section 7.2) will determine whether the event requires expedited reporting **in addition** to routine reporting.

Information regarding the occurrence of adverse events will be collected from the time the subject signs the informed consent form and throughout their participation in the study, including a period of 30 days after the last dose of study drug (data on serious adverse events (SAEs) will be collected until resolution of the event unless otherwise noted). Serious adverse events occurring outside the 30-day follow-up period, which are assessed as related to study drug, should be reported to Amgen, along with any SAE that the investigator feels should be reported.

7.1 Adverse Event Definitions

An **adverse event** (AE) is any untoward medical occurrence associated with the use of a drug in humans, whether or not considered drug related. An adverse event can be any unfavorable and unintended sign including clinically significant abnormal laboratory finding, symptom, or disease temporally associated with the use of the drug, without any judgment about causality. This includes any newly occurring event or previous condition that has increased in severity or frequency since the administration of drug.

Following surgical resection of the tumor, non-serious adverse events consistent with an expected post-operative course will not be reported unless attributable to the study drug and/or meet the seriousness criteria.

An adverse event is considered a **serious adverse event** (SAE) if it results in any of the following outcomes:

- 1) Results in death
- 2) Is a life-threatening event (ie, its occurrence places the patient or subject at immediate risk of death)
- 3) Requires inpatient hospitalization or prolongation of existing hospitalization for ≥ 24 hours
- 4) Results in a persistent or significant incapacity or substantial disruption of the ability to conduct normal life functions
- 5) Is a congenital anomaly/birth defect
- 6) Is an important medical event that may not result in death, be life threatening, or require hospitalization but may be considered serious when, based upon medical judgment, may jeopardize the patient or subject and may require medical or surgical intervention to prevent one of the outcomes listed in this definition.

Suspected Adverse Reaction

Suspected adverse reaction means any adverse event for which there is a reasonable possibility that the drug caused the adverse event. For the purposes of IND safety reporting, ‘reasonable possibility’ means there is evidence to suggest a causal relationship between the drug and the adverse event. A suspected adverse reaction implies a lesser degree of certainty about causality than adverse reaction, which means any adverse event caused by a drug.

Unexpected Adverse Events

An adverse event is considered “unexpected” if it is not listed in the table of expectedness within the Investigator Brochure or is not listed at the specificity or severity that has been observed; or, if an Investigator Brochure is not required or available, is not consistent with the risk information described in the general investigational plan or elsewhere in the current application.

When talimogene laherparepvec is administered in combination with 1 or more approved antineoplastic agents, the expectedness determination should take into account the labeling of each specific marketed drug taken in combination based upon reference documents which will be included or referenced in the clinical study protocol. The labeled events should, in general, be

considered expected for at least one of the drugs in the combination. The contribution of talimogene laherparepvec to the severity or frequency of the events is currently unknown. See Section 1.2.2 for adverse drug reactions that could be reasonably assumed to be associated with talimogene laherparepvec.

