3. OBJECTIVES

| Primary Objectives | Corresponding Primary Endpoint |
|---|--------------------------------|
| Phase 1b: To determine the safety and tolerability of neoadjuvant talimogene laherparepvec in combination with preoperative EBRT as assessed by incidence of dose-limiting toxicities (DLT) in subjects with locally advanced high grade soft tissue | Incidence of DLTs |

| | |
|--|---|
| sarcomas. | |
| Phase 2: To estimate the efficacy of neoadjuvant talimogene laherparepvec and radiotherapy as assessed by the pathological complete response rates (pCR) in subjects with histologically confirmed diagnosis of locally advanced STS that is unresectable with clear wide margins, for which preoperative radiotherapy is considered appropriate. | pCR rate - the proportion of subjects with pathologic tumor necrosis $\geq 90\%$ |
| Secondary Objectives Further assess the safety of talimogene laherparepvec given concurrently with preoperative external beam radiation in sarcoma patients. To estimate: 
• Overall response rate (ORR)• Time to progression (TTP)• Overall survival (OS) | Corresponding Secondary Endpoint Type, incidence, severity, and relatedness of AEs ORR – The proportion of subjects with a complete or partial response. TTP - Time from first day of study treatment to first documented disease progression Overall survival – Time from first day of study treatment to death due to any cause. |

For this study, pCR will be defined as $\geq 90\%$ tumor necrosis following concurrent radiation therapy and talimogene laherparepvec.

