7.7 Expedited Adverse Event Reporting

7.7.1 Expedited Reporting Guidelines

Reporting to the HCCC DSMC per DSMP (Appendix E)

Reporting Requirements to AMGEN

Safety Reporting to Amgen

The Sponsor/Investigator is responsible for compliance with expedited reporting requirements for serious, unexpected and related adverse events (SUSARs), for generation of SAE reports including narratives, and for periodic reporting to Amgen of SAEs as outlined in **Table 2** and **Table 3** below. Individual safety reports (Table 2) should be accompanied by the Fax Cover Form and sent to Amgen Global Safety, utilizing the fax or email information provided on the cover page. Aggregate safety reporting (Table 3) including listings, tabulations and summary reports should be scanned and accompanied by the Fax Cover Form and sent to Amgen NASCR, utilizing the email information provided on the cover page.

In addition to the requirements outlined in Table 2 and 3, Sponsor/Investigators are required to report **direct exposures** to talimogene laherparepvec (e.g., needle stick, splash back) of herpetic illness and **all suspected herpetic events** (refer to Section ‘Accidental Exposures to Talimogene Laherparepvec and Herpetic Events’).

Table 2. Reporting Requirements for Interventional Studies

| Safety Data | Timeframe for Submission to Amgen |
|--|--|
| Suspected Unexpected Serious Adverse Reaction (SUSARs) | Individual reports sent to Amgen at time of expedited reporting to IRB and/or FDA. |
| Serious Adverse Events (SAEs) (related) | Individual reports sent to Amgen at time of expedited reporting to IRB and/or FDA. |
| Pregnancy/Lactation | Individual reports sent within 10 days of Sponsor/Investigator awareness. |

Individual reports should be faxed to [name] or scanned and sent via email to [contact].

Table 3. Aggregate Reports:

| Safety Data | Timeframe for Submission to Amgen |
|---|---|
| Adverse events (all serious and non-serious adverse events, regardless of relatedness) | Line listing and summary tabulation of all adverse events sent annually AND at end of study |
| US IND Annual Safety Report | Annually |
| Other Aggregate Analyses (any report containing safety data generated during the course of the study) | At time of ISS sponsor submission to any body governing research conduct (e.g., RA, IRB, etc.) |

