12. STATISTICAL CONSIDERATIONS

12.1 Study Design/Endpoints

Phase Ib

| Number of Patients with DLT at a Given Talimogene Laherparepvec Dose | Decision Rule |
|--|---|
| ≥ 2 | Dose level will be declared toxic. If this is the lowest dose level, stop the study due to excessive toxicity; otherwise enter three additional patients at the next lowest dose level. |
| ≤ 1 out of 3 | Enter three more patients at this dose level. |
| ≤ 1 out of 6 | This is the recommended Phase II dose. |

Up to 6 patients will be treated at each dose level. The recommended Phase II dose will be defined as the highest dose level for which at most 1 out of 6 patients experience a DLT.

Phase II

The primary objective of the Phase II portion of this study is to evaluate the preliminary evidence of anti-tumor activity of talimogene laherparepvec in combination with external beam radiation therapy. The primary endpoint of interest is pathologic complete response (pCR) rate defined as the proportion of subjects with pathologic tumor necrosis of $\geq 90\%$. Estimates of historic pCR based on tumor necrosis $\geq 90\%$ for the treatment of soft tissue sarcomas with external beam radiation therapy are not available in the current literature. However, a pCR rate of 30% would be considered unacceptable for the proposed combination treatment whereas a pCR of 55% or more is considered clinically important. Sample size requirements are based on an optimal Simon two-stage design with 80% power and a significance level of 5%. Nine (9) patients will

be enrolled in the first stage, and the study will be terminated if 3 or fewer respond. Otherwise, an additional 26 patients will be enrolled in the second stage. If 15 or more of the 34 total patients respond, the treatment will be deemed worthy of further investigation. This design has an expected sample size of 16.0 and a 0.73 probability of early termination.

Data Analysis and Reporting

The number and severity of all adverse events will be summarized by simple descriptive statistics. pCR and ORR (CR+PR) rate point estimates and 95% exact confidence intervals will be reported. For TTP (time from first day of study treatment to first documented disease progression) and OS (time from first day of study treatment to death due to any cause), survival curves using the Kaplan-Meier method will be constructed. Estimates along with 95% confidence intervals will be reported.

REFERENCES

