- Serious adverse events will be entered directly into an OnCore SAE report by the research team. OnCore will send an automatic notification to the DSMC Chair/acting Chair and staff for review.
- The DSMC utilizes a risk-based monitoring approach. The trial's research records will be monitored at minimum twice per year. Monitoring may be done more frequently depending on the protocol, risks to subjects, reported serious/adverse events, patient population and accrual rate. Records for a minimum of 25% of subjects will be monitored for the entire study.

Monitoring will involve the following:

- review eligibility of patients accrued to the study,
- check for the presence of a signed informed consent,
- determine compliance with protocol's study plan,
- determine whether SAEs are being appropriately reported to internal and external regulatory agencies,
- compare accuracy of data in the research record with the primary source documents,
- review investigational drug processing and documentation,
- assess cumulative AE/SAE reports for trends and compare to study stopping rules.

- **Routine Adverse Event Reporting**

For non-serious Adverse Events, documentation must begin from the time the subject signs the informed consent document and continue through the 30-day follow-up period after the last dose of study drug.

Collected information should be recorded in the electronic/Case Report Forms (eCRF/CRF) for that subject. A description of the event, its severity or toxicity grade (according to [NCI's Common Toxicity Criteria \(CTCAE\)](#)), onset and resolved dates (if applicable), and the relationship to the study drug should be included. Documentation should occur in real time. The principal investigator has final responsibility for determining the attribution of the event as it is related to the study drug.

-
- **Serious Adverse Event Reporting**

For any experience or condition that meets the definition of a serious adverse event (SAE), recording of the event must begin after signing of the informed consent and continue through the 30 day follow-up period after treatment is discontinued.

Investigators must report to the DSMC any serious adverse events (SAE), whether or not they are considered related to the investigational agent(s)/intervention (21 CFR 312.64). SAEs must be reported via an OnCore SAE Report within 24 hours of learning of the event.

An adverse event is considered **serious** if it results in ANY of the following outcomes:

1. Death

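### Section 7.1's post-operative exemption conflicts with Table 3's all-events rule, so some non-serious treated-site wound events may go uncounted in the secondary safety incidence

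*Combined protocol and SAP*

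**What the plan says.** Section 7.1 defines an adverse event broadly, "without any judgment about causality". The paragraph after the definition makes an exception for the time after surgery: "non-serious adverse events consistent with an expected post-operative course will not be reported unless attributable to the study drug and/or meet the seriousness criteria". The protocol does not define an expected post-operative course.

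Four other places set the scope of adverse event data, and none refers to this exception:

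- Section 7.7.1, Table 3 (aggregate reports to Amgen): "Adverse events (all serious and non-serious adverse events, regardless of relatedness", as a line listing and tabulation each year and at study end.
- Section 12.1: "The number and severity of all adverse events will be summarized by simple descriptive statistics".
- Section 7, opening text: collection from consent onward, "including a period of 30 days after the last dose of study drug".
- Appendix E, in its part on routine reporting, states: "For non-serious Adverse Events, documentation must begin from the time the subject signs the informed consent document and continue through the 30-day follow-up period".

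The secondary safety objective in Section 3 is to "Further assess the safety of talimogene laherparepvec given concurrently with preoperative external beam radiation in sarcoma patients", with the endpoint "Type, incidence, severity, and relatedness of AEs".

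Two further passages bear on wounds. Section 5.2.4 lists wound complications of any grade among the acute radiation effects and expects them in about one third of patients. Section 7.4 names impaired healing at the injection site as an important potential risk of the drug, to be watched very closely, above all with concurrent radiation.

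**The concern.** The exemption filters on drug attribution alone, while the secondary objective is the safety of the drug given with radiation. A non-serious wound event put down to radiation or surgery could therefore be left out, although it belongs to the experience the objective describes. The trial has one arm, so no comparator shares the omission, and any omission moves the recorded incidence in one direction only: down.

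Staff who follow Section 7.1 and staff who follow Table 3 would also report different events. Nothing scheduled later would recover a missed one. The study calendar's only adverse event review after surgery is the 30-day safety visit, and long-term follow-up collects recurrence and survival only (Sections 5.5 and 10.3).

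**Working it through.** The plan gives no figure to reproduce here. The check compares text and then gives an order of magnitude.

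**Step 1. Scope, side by side.**

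| Place | Verb | Filter on relatedness? | Relation to the exemption |
|---|---|---|---|
| 7.1, exemption | report | yes, drug only, for non-serious events | – |
| 7.7.1, Table 3 | submit listing and tabulation | expressly none | direct conflict |
| 12.1 | summarize all | none stated | exemption not carried over |
| 7, opening text | collect | none stated | softer: collecting is not reporting |
| Appendix E | document | none stated | softer, but placed under a reporting heading |

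**Step 2. Does the exemption concern expedited reporting only?** Section 7 says that 7.1 and 7.2 help decide what needs expedited reporting. But the exemption covers only non-serious events. The special or expedited routes in Section 7.7 and Appendix E concern serious events, pregnancy or lactation, accidental exposures and herpetic events. An ordinary non-serious post-operative event has no expedited duty to waive, so the sentence has practical content only for routine reporting.

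**Step 3. Does part of the adverse event period follow surgery?** Injections continue until surgery, and the period ends 30 days after the last one. With a gap of g days between last injection and surgery, 30 − g post-operative days are covered. Assume g lies between 0 and 14; 14 is a last injection at week 12 with surgery at week 14. Then:

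- 30 − 0 = 30 days and 30 − 14 = 16 days;
- with the +7 day visit allowance, 37 and 23 days.

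This range is conditional. If injections stop early, g is longer and few or no post-operative days may be covered.

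**Step 4. Which events can be lost?** An event must meet all four conditions: it occurs after surgery and inside the period; it is non-serious; it is judged not attributable to the drug; and it is judged consistent with an expected post-operative course.

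**Step 5. Scale.** Expected patients with any wound complication = N × p. The rate p is one third (Section 5.2.4) or 25% to 44% (retrospective reviews cited in Section 1.3). N is 28 (Section 5.1) or 34 (Section 12.1); the stage sizes in 12.1 add to 9 + 26 = 35.

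| N | p = 25% | p = 1/3 | p = 44% |
|---|---|---|---|
| 28 | 7.0 | 9.3 | 12.3 |
| 34 | 8.5 | 11.3 | 15.0 |
| 35 | 8.8 | 11.7 | 15.4 |

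These are Phase 2 patients. Phase 1b adds up to 6 per dose level. Each patient left unrecorded lowers the rate by 1/28 = 3.6 or 1/35 = 2.9 percentage points. The table counts all wound complications, not the subset meeting the four conditions in Step 4, and the documents give no figure for that subset.

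**The case against.** **A specific exception qualifies the general rule.** The exemption sits in the same section as the broad definition, and all events in Section 12.1 can be read as all events reportable under Section 7. This stands for the definition and for 12.1: what is missing there is a cross-reference. It does not stand for Table 3, which expressly rules out the relatedness filter that Section 7.1 applies.

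**Not reported is not the same as not collected.** If Section 7.1 governs onward reporting only, the events stay in the database under Section 7 and Appendix E, and the secondary incidence loses nothing. This stands as a possible reading. But Appendix E puts the recording of non-serious events on case report forms under its routine reporting heading, so the opposite reading is also reasonable.

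**Wound events are unlikely to be judged unrelated.** Section 7.2 asks only whether the drug may have played a part, and its scale includes a *possible* category. Appendix D lists delayed wound healing as a drug reaction, and the expected-toxicities list in the monitoring plan includes wound complications and delayed healing at the injection site. Most of this stands and makes the loss smaller. What remains is that Section 7.1 does not say whether *possible* counts as attributable.

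**The stronger reading.** A reader might infer that the one third of patients expected to have wound complications would vanish from the safety results. The documents do not support that. Serious events and drug-attributed events are kept, and the text does not settle whether a wound complication is part of an expected post-operative course.

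**Conclusion.** The conflict between Section 7.1 and Table 3 is real. The exemption is also not carried into Section 12.1, the opening of Section 7 or Appendix E. An undercount of the secondary adverse event incidence is possible, not certain. It requires that not reported is taken as not recorded, and it is confined to non-serious treated-site or resected-site wound events judged due only to radiation or surgery. Any such omission lowers the incidence.

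The size cannot be derived. The figures of about 9 of 28 or 12 of 35 patients, or 7 to 12 and 9 to 15 over the cited range, show how common wound complications are expected to be; they do not estimate the loss.

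A reader might also infer that the primary endpoints are compromised. They are not: the DLT period runs through week 8, before surgery at weeks 12 to 14, and pCR is read from the resected tumor. No decision rule uses this incidence. The point is a cheap improvement of minor severity.

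**What to change.** Reconcile Section 7.1 with the opening of Section 7, Table 3, Section 12.1 and Appendix E:

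1. State in Section 7.1 that wound complications and impaired healing at the treated or resected site are outside the exemption. Record them with grade and attribution, whatever the attribution, within the existing adverse event period and at the existing 30 (+7) day safety visit.
2. State that attributable includes *possible*.
3. Keep the exemption for other routine post-operative events, and cross-reference it in Table 3, Section 12.1 and Appendix E.

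Two additions are optional: a definition of an expected post-operative course, and a descriptive wound-complication rate with an exact 95% confidence interval, noting that follow-up is timed from the last injection and so differs between patients after surgery.

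The core change costs two statements in Section 7.1, three cross-references and a few more non-serious events to enter. It needs no new visit, no longer adverse event period and no formal test.

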7.2 Adverse Event Characteristics

CTCAE term (AE description) and grade: The descriptions and grading scales found in the revised NCI Common Terminology Criteria for Adverse Events (CTCAE) version4.0 (Appendix E) will be utilized for AE reporting. If specific grading is not available in the CTCAE for a particular AE's severity/intensity, the Investigator is to revert to the general definitions of Grade 1 through 5 and use his/her best medical judgment. The 5 general grades are: Grade 1 = mild, Grade 2 = moderate, Grade 3 = severe, Grade 4 = life-threatening or disabling, Grade 5 = death related to AE.

Attribution of the AE:

Investigators are required to assess whether there is a reasonable possibility that talimogene laherparepvec caused or contributed to the adverse event. The following general guidance may be used.

- Definite – The AE is *clearly related* to the study treatment.
- Probable – The AE is *likely related* to the study treatment.
- Possible – The AE *may be related* to the study treatment.
- Unlikely – The AE is *doubtfully related* to the study treatment.
- Unrelated – The AE is *clearly NOT related* to the study treatment.

7.3 Comprehensive Adverse Events and Potential Risks List (CAEPR)

All necessary supportive care shall be available to subjects. Additional treatment modifications should be considered depending upon the subject's clinical situation. Talimogene laherparepvec treatment should be continued based on the potential risk/benefit assessment of the subject.

